SYNOPSIS

Clinical Protocol IM128027

Protocol Title: A Phase 2, Multi-Center, Randomized, Double-Blind, Placebo-Controlled Study to Evaluate the Safety and Efficacy of BMS-931699 vs Placebo on a Background of Limited Standard of Care in the Treatment of Subjects with Active Systemic Lupus Erythematosus

Investigational Product(s), Dose and Mode of Administration, Duration of Treatment with Investigational Product(s): BMS-931699 (active) or lulizumab pegol, administered subcutaneously, is formulated at 12.5 mg/mL and is provided as a liquid in single-use vials. Four treatments will be administered along with placebo treatment: 12.5 mg weekly, 12.5 mg every other week (EOW), 5 mg EOW and 1.25mg EOW, on a background of limited standard of care medications. The dose levels may be modified based on the interim analysis results. The study will comprise a short-term period (Part 1 and Part 2) and a long-term extension (LTE) period. Treatment duration will be up to 24 weeks (169 days) in the short term period. Subjects completing the short term period on study medication may be eligible to enter the LTE period. At the time of writing there is no defined end date to the long-term extension period, however, the LTE provision may be further adjusted based on results from the ongoing lulizumab development program.

Study Phase: Phase 2

Research Hypothesis: BMS-931699 will have greater clinical efficacy compared to placebo on the British Isles Lupus Assessment Group (BILAG)-based Composite Lupus Assessment (BICLA) score, when added to stable background standard of care in subjects with active manifestations of systemic lupus erythematosus (SLE) including, at a minimum, elevated antinuclear antibodies, arthritis, and/or cutaneous manifestations satisfying the BILAG "A" or "B" criteria.

Objectives for the short-term period:

Primary Objective:

To compare the proportion of subjects who achieve BICLA response (BICLA response rate) at Day 169.

Secondary Objectives:

For Part 1 only:

- To evaluate the safety and receptor occupancy (RO) when 6 to 10 subjects per arm reach 29 days (4 weeks).

For both Part 1 and Part 2:

To assess:

- The safety and tolerability of treatment with BMS-931699 in subjects with active SLE
- The proportion of patients who meet response criteria for the SLE Responder Index (SRI) (4), SRI(5) and SRI(6) at Day 169 following 24-week treatment with BMS-931699 or placebo administered on a stable background therapy.
- The proportion of patients with SLE Responder Index [SRI(4), SRI(5) and SRI(6)] at Day 85 following 12-week treatment with BMS-931699 or placebo administered on a stable background therapy.
- The proportion of subjects with BICLA response at Day 85 following 12-week treatment with BMS-931699 or placebo administered on a stable background therapy
- The improvement in the extent of cutaneous and mucous membrane activity, as measured by the Cutaneous Lupus Erythematosus Disease Area and Severity Index (CLASI) at Day 85 and Day 169
- Joint tenderness and swellings by American College of Rheumatology (ACR)28 criteria at Day 85 and Day 169
- The other indices of SLE activity measured at Days 29, 57, 85, 113, 141 and 169 including:
 - The change from baseline in overall BILAG-2004 score. A major response is defined as described in Yee et al 2010 (A=12; B=8; C=1; D/E=0).
 - The change in overall Systemic Lupus Erythematosus Disease Activity Index 2K score (SLEDAI 2K)

- The change from baseline in Physician's Global Assessment of disease activity (MDGA) score
- The systemic exposure of BMS-931699 in subjects with SLE
- The cumulative corticosteroids use and immunosuppressants use over time
- The immunogenicity of BMS-931699
- Serum biomarkers C3, C4, anti-double-stranded deoxyribonucleic acid (anti-dsDNA), anti-nuclear antibody (ANA) and other autoantibodies at Day 85 and Day 169
- The pharmacodynamics (PD) of BMS-931699, including assessments potentially associated with target engagement (including receptor occupancy [RO]).

Objectives for the long-term extension period:

[figure not shown]
Assess the long term clinical safety, tolerability and efficacy of lulizumab pegol.

Study Design:

[figure not shown]
Phase 2, parallel-arm, randomized, double-blinded, multicenter, international study, with an adaptive design. Dose arm(s) may be adapted based on results of the planned interim analyses from Part 1 and Part 2, as follows:

- Safety and RO interim analysis: safety and RO analysis will be performed when approximately 6 to 10 subjects per arm have reached Study Day 29. Based on the results of this analysis, dose arm(s) may be adjusted or may be dropped.
- Interim analysis for futility and dose adaptation on BICLA response, SRI response, ACR28 and some SLE biomarkers (such as auto-antibodies, complement levels, etc.) with possible exploratory exposure response analysis, will be performed when approximately 30 subjects per arm (including subjects from Part 1 and Part 2) have reached Study Day 85 (12 weeks) of treatment or have discontinued prior to reaching study Day 85. Analysis will be performed by an unblinded Sponsor team, while maintaining blind at the site and subject level. Based on the results, the dose levels and sample size may be modified.
- Ongoing assessment of safety will be performed by an independent Data Monitoring Committee (DMC) and an internal unblinded safety monitoring team. Both entities may make recommendations to the Sponsor regarding conduct of study and dose adjustment based on safety observations.

Overall study design

[figure not shown]

Study Design Schematic - Short-term Period (Part 1)

Will not apply to subjects entering LTE.

[figure not shown]
Study Design Schematic - Short-term Period (Part 2)

* Treatment arm may or may not be included based on Part 1 Day 29 Interim Analysis.

Will not apply to subjects entering LTE.

Study Design Schematic - Long-term extension Period

* Treatment arm may or may not be included based on Interim Analyses.

⊗ Subjects in the placebo arm will be re-randomized to existing active treatment arms at Day 169.

FU Day 42 to occur after last dose of study medication, whether last dose is in short term or long term periods.

Duration of Study:

Short-term Period: 28 days (4 weeks) of screening, 168 days (24 weeks) of treatment, 42 days (6 weeks) of safety follow-up, for a total of approximately 238 days (34 weeks). Subjects randomized into either Part 1 or Part 2 will be treated for up to 24 weeks and will have the same procedures performed and will follow the same visit schedule. If subject is eligible and opts to continue into LTE, the 42-day follow-up visit will not be performed after the short-term period is completed and subject will enter LTE directly. If subject opts not to enter LTE then a follow-up visit will be completed 42 days after end of treatment. At the time of writing there is no defined end date to the long-term extension period, however, the LTE provision may be further adjusted based on results from the ongoing lulizumab development program. Subjects discontinuing treatment during the LTE period will complete the follow-up visit approximately 6 weeks after receiving their last dose of study medication.

Number of Subjects:

Approximately 450 subjects will need to be screened to randomize approximately 350 subjects. Utilizing a 1:1:1:1:1 randomization scheme resulting in approximately 70 subjects in the each treatment arm. If the day 85 interim analysis suggests an additional dose arm at a lower dose level needs to be added, then up to 40 additional subjects may be randomized.

Approximately 125 sites will participate in this study, which will be conducted globally and should include, but will not be limited to, participation of countries located in North America and Europe.

Study Population: Male and female subjects, ages 18-70 years inclusive, satisfying the SLE classification criteria of the American College of Rheumatology (1982), as revised by the College in 1997, with elevated titer of anti-nuclear antibodies at Screening, active features of SLE, including at least one adjudicated BILAG B or greater due to arthritis and/or inflammatory skin disease. Unless intolerant, subjects must be on background therapy for 12 weeks, on a stable dose for at least 8 weeks, with at least one steroid sparing agent, including azathioprine (AZA), leflunomide, methotrexate (MTX), anti-malarial agents, mycophenolate mofetil/ mycophenolic acid, which must remain on stable dose throughout the study. Prednisone is not required; however, if subject is taking prednisone (or prednisone-equivalent), the maximum dose must not exceed 30mg/day of prednisone (or prednisone equivalent) at screening for a subject to be eligible and must be at a maximum of 10mg/day for at least 5 days prior to Day 1. Subjects must not have SLE manifestations or other disorders expected to require increase in corticosteroids (CS) during the study.

Women of childbearing potential (WOCBP) must not be nursing or pregnant and must be using an acceptable method of contraception for at least 4 weeks before dosing. WOCBP must have a negative pregnancy test within 24 hours prior to dosing with study medication

Study Drug: includes both Investigational [Medicinal] Products (IP/IMP) and Non-investigational [Medicinal] Products (Non-IP/Non-IMP) as listed:

Study Drug for IM128027

Medication	Potency	IP/Non-IP
BMS-931699	12.5mg/mL	IP

Study Assessments:

- Efficacy assessments: will include BILAG-2004 Index, SLEDAI 2K, Physician's Global Assessment of Disease Activity (MDGA), Subject's Global Assessment of Disease Activity (PGA), ACR28 - joint count, FACIT - F, CLASI, SLICC/ACR Damage Index, SF-36, Coomb's test-direct.
- Safety assessments will be based on medical review of adverse event reports and the results of vital sign measurements, ECGs, physical examinations, and clinical laboratory tests. The incidence of observed adverse events will be tabulated and reviewed for potential significance and clinical importance. Ongoing assessment of safety will be performed by an independent Data Monitoring Committee (DMC). The DMC may make recommendations to the Sponsor regarding conduct of study based on safety observations.

- Pharmacokinetic parameters: Ctrough will be derived from serum BMS-931699 concentration versus time data.

- [REDACTED]

[REDACTED]

[REDACTED]

Statistical Considerations:

Sample Size: The sample size calculation is based on power to compare the proportion of subjects who achieve BICLA response (the BICLA response rate) at Day 169 between BMS-931699 and placebo arms. With a one-sided continuity corrected chi-squared test at significance level 0.05, data from 70 randomized and treated subjects per arm will provide at least 89% power to detect a 25% increase in the BICLA response rate in the active treatment arms (ie. 50% response rate in BMS active arms) compared to the placebo and provide 74% power to detect 20% increase in the BICLA response rate in the active treatment arm (ie, 45% response rate in BMS active arm) compared to the placebo, assuming that the placebo arm has 25% response rate which is reasonable based on the EMBLEM phase 2 trial result.¹ No adjustment will be made for multiplicity. Subjects who discontinue treatment/study prior to Day 169 will contribute to the data that will be analyzed for BICLA response at Day 169 (discontinuation will indicate no BICLA response). Therefore, no adjustment will be made for discontinuations.

The primary efficacy analysis will be conducted on all randomized patients who received at least one dose of the study drug. In order to get 70 randomized and treated subjects per arm, an adequate numbers of subjects need to meet the inclusion/exclusion criteria at screening.

If the interim analysis for futility and dose adaption suggests an additional dose arm at a lower dose level needs to be added, then up to 40 additional subjects may be randomized.

Endpoints for Short term Period:

Primary Endpoint

- Proportion of subjects who achieve BICLA response (BICLA response rate) at Day 169.

Secondary Endpoints

Safety

- Incidence and severity of all Adverse Events (AEs), Serious AEs (SAEs), and pre-established Events of Special Interest
- Incidence and severity of clinically significant changes in vital signs
- Incidence and severity of clinically significant ECG abnormalities
- Incidence and severity of clinically significant abnormalities in general laboratory tests

Efficacy

- Proportion of subjects who meet response criteria for the SLE Responder Index [SRI(4), SRI(5) and SRI(6)] at Day 169
- Proportion of subjects who meet response criteria for the SLE Responder Index [SRI(4), SRI(5) and SRI(6)] at Day 85
- Proportion of subjects with BICLA response at Day 85
- Change from baseline in CLASI score at Day 85 and Day 169
- Percentage of subjects with an improvement of >4 or a decrease of >50% from baseline in their CLASI score at Day 85 and Day 169

- Change from baseline in arthritis, as assessed by ACR28-joint count of tender and swollen joints at Day 85 and at Day 169
- The change from baseline in the following other indices SLE activity over time:
 - The overall BILAG-2004 score
 - The overall SLEDAI-2K score
 - The overall MDGA score
- The cumulative corticosteroid and immunosuppressant use over time

Pharmacokinetic

- Ctrough: Trough level serum concentration of BMS-931699 at time points specified in Table 5.5.1-1.

Immunogenicity

- Proportion of subjects with BMS-931699 induced antibody response over time points specified in Table 5.5.1-1.

Endpoints for Long term Extension Period:

During the LTE period, the following endpoints will be assessed cumulatively (safety) and over time (efficacy).

Safety Endpoints

- Incidence and severity of all Adverse Events (AEs), Serious AEs, and pre-established Events of Special Interest
- Incidence and severity of clinically significant abnormalities in general laboratory tests

Efficacy Endpoints

- Proportion of subjects who achieve BICLA response (BICLA response rate)
- Proportion of subjects who meet response criteria for the SLE Responder Index (SRI) [SRI(4), SRI(5) and SRI(6)]
- CLASI score
- ACR 28 joint count of tender and swollen joints
- Overall BILAG-2004 score
- Overall SLEDAI-2K score
- Overall MDGA score
- The cumulative corticosteroid and immunosuppressant use
- Proportion of patients reaching a Major Clinical Response and Partial Clinical Response
- Fatigue, based on the FACIT
- Quality of life, based on SF-36

Pharmacokinetic Endpoints

- Ctrough: Trough level serum concentration of BMS-931699 at time points specified in Section 5.5.

Immunogenicity

- Proportion of subjects with BMS-931699 induced antibody response

Analyses for the Short-term Period:

Primary analysis:

The Chi-square tests will be used to compare the BICLA response rates at Day 169 between each of the active treatment arms and the placebo arm. The Chi-square p-value will be provided for each comparison between the active treatment and the placebo arm. In addition, the difference of the response rates between each active treatment and placebo will be estimated and their corresponding 90% confidence interval will be calculated. No adjustment will be made for multiplicity.

Secondary analysis:

Efficacy analysis:

- Proportion of subjects who meet response criteria for the SLE Responder Index [SRI(4)], SRI(5) and SRI(6)] at Day 169
- Proportion of subjects who meet response criteria for the SLE Responder Index [SRI(4)], SRI(5) and SRI(6)] at Day 85
- Proportion of subjects with BICLA response at Day 85
- Percentage of subjects with an improvement of > 4 or a decrease of > 50% from baseline in their CLASI score at Day 85 and Day 169

For each of the above endpoints, the estimate and its corresponding 90% confidence interval will be calculated for the difference of the proportions between each active treatment arm and the placebo arm at the specified visit, similar to the primary analysis.

For each of the following endpoints, the mixed effect model will be fit with treatment and visit as the fixed effects and measurements within each subject as the repeated measurements. The baseline value will be added into the model as a covariate if necessary. Based on the mixed effect model, the estimate and 90% confidence interval will be calculated for the difference between each active treatment and the placebo at each specified visit.

- Change from baseline in CLASI score at Day 85 and Day 169
- Change from baseline in arthritis, as assessed by ACR28-joint count of tender and swollen joints at Day 85 and at Day 169
- The change from baseline in the following other indices SLE activity over time:
 - The overall BILAG-2004 score
 - The overall SLEDAI-2K score
 - The overall MDGA score

In addition, the cumulative corticosteroid and immunosuppressant use over time will be summarized.

Safety analysis:

All recorded adverse events will be listed and tabulated by system organ class, preferred term and treatment. Vital signs and clinical laboratory test results will be listed and summarized by treatment. Any significant physical

examination findings, and clinical laboratory results will be listed. ECG readings will be evaluated by the investigator and abnormalities, if present, will be listed. The pre-established Events of Special Interest will be listed and summarized.

PK analysis:

Ctrough will be summarized by dose and study day.

Immunogenicity analysis

Proportion of subjects with BMS-931699-induced antibody response and titers over time will be summarized.

Interim analysis:

Interim Analysis for Safety/RO at Day 29

When at least 6 subjects per arm have reached Day 29, an interim analysis (IA) for safety and RO will be performed. The safety analysis will focus on incidence and severity of all adverse events (AEs), serious AEs and pre-established Events of Special Interest such as infection AEs and any other safety analysis requested by DMC. For RO: the median RO at Day 29 for each treatment arm will be calculated. Based on the results of this interim analysis, a decision will be taken regarding the doses that will be carried forward into Part 2 of the study. Specifically, dosing regimens originally included in Part 1 may be discontinued and/or new dosing regimens may be added according to the following criteria:

Safety:

The DMC in conjunction with an unblinded internal monitoring team may require one or more doses to be discontinued if stopping criteria are met or other safety signals arise that the Medical Monitor and/or DMC consider of sufficient concern.

Receptor Occupancy:

- If median RO of any dose is < 20%, the sponsor may consider dropping that dose;
- If the median RO for all doses is > 90%, the sponsor may consider adding or replacing a dose in Part 2 of the study to ensure an adequate pharmacodynamic range (dose not to exceed 12.5 mg weekly).

Dose decrease and/or reduction of frequency of administration may also be considered if RO results fall outside the parameters indicated above. This adjustment may occur for safety reasons or in case unforeseen RO profiles observed in SLE patients. The decision to adjust dose and/or frequency will be taken after review of the data by the clinical team.

Interim analysis for futility and dose adaptation at Day 85:

After 30 subjects per treatment arm (including the subjects from Part 1) have completed at least 84 days of the treatment period or discontinued the treatment, an interim analysis will be conducted to assess the futility of the BMS-931699 dose arms and the overall safety. The results of the interim analysis will be reviewed by an unblinded sponsor team who will provide recommendations to the blinded study team. The blinded study team will make the decision. The unblinded BMS team may recommend to:

- Maintain the current design;
- Drop a certain dose arm(s) and equally randomize the remaining unallocated subjects to the remaining arms;
- Stop the study if all dose arms need to be dropped for safety or futility reasons.

The interim analysis for futility and dose adaption will be performed on the BICLA response at Day 85 and Day 169, of those 30 subjects per arm who have completed 85 days of treatment or discontinued the treatment, using

a Bayesian predictive approach.² This analysis assumes that the BICLA response at Day 85 and at Day 169 in the subjects who have not yet been observed will be similar to those observed for the subjects included in the interim analysis at Day 85 and Day 169, respectively. As such, the unobserved data will be simulated from the predictive distribution conditional on the interim data and the prior distribution of the treatment difference (using a non-informative prior). Under the Bayesian framework, the posterior distribution of the treatment difference (BMS-931699 active dose – Placebo) will be constructed to determine the predictive probability of a successful outcome (ie, reach statistical significance) at Day 169. Based on computer simulations of the operating characteristics of the study design, the futility threshold in this interim analysis is set to 0.2. For the comparison of interest, if the predictive probability of a successful outcome at the planned end of the trial falls below 0.2, that BMS-931699 dose arm is deemed futile in terms of BICLA response. However, the final futility will also incorporate the results from SRI(4), ACR28 and some biomarkers (C3, C4, ANA and anti-dsDNA).

The proposed stopping rules at the interim analysis, based on the futility assessment and the overall safety assessment, are as follows:

- Rule 1: Drop the futile dose arm(s) and the dose arm cannot be dropped until the lower dose arm has been dropped.
- Rule 2: Drop the dose arm(s) with safety issues identified;
- Rule 3: If safety issues are identified in all dose arms or all dose arms are futile, stop the study.

In case dosing arms are dropped following the interim analysis, the remaining unallocated subjects will be randomized into the remaining arms.

If the predictive probability of success for each active arm versus placebo is greater than or equal to 0.9, then the BMS team may also recommend adding an additional dose arm at lower dose level than current active doses to explore a suboptimal dose.

In that case, the remaining unallocated subjects with up to 40 additional subjects will be randomized into the remaining arms and the new dose arm based on the new randomizations schedule.

Analyses for the long-term extension period:

The LTE period starts when a subject receives at least one post Day 169 dose. The analysis based on this period is descriptive in nature.

Populations of Analysis

All Subjects who received at least one dose post Day 169.

Demographics and Baseline Characteristics

Categorical parameters will be summarized using frequency counts and percentages. Continuous parameters will be summarized through means, SD, median, and range. The baseline (Day 1) is defined as the start of study medication (the same as baseline in Double-blind period). The baseline results will be based on LTE analysis population.

Efficacy Analyses

For continuous secondary endpoints (e.g. SLEDAI, MDGA etc.) point estimates and 90% confidence intervals for mean change from baseline to subsequent time points (in LTE period) within each treatment groups will be provided. For binary endpoints (BICLA Response, SRI(X) etc.), point estimates and 90% confidence intervals (CIs) will be provided using normal approximation within each treatment group. The assessment windows for LTE period will be based on the first LTE dose date; the baseline to assess responses or changes still refers to the Day 1 assessment (the same as baseline in Short-term Period). The results will be presented by treatment groups. All Analyses will be based on as-observed data; hence no imputation will be implemented. No statistical testing including p-value computation will be performed.

Safety Analyses

The evaluation of long term safety of the selected dose(s) will be based on clinical adverse events, vital signs and laboratory abnormalities reported during the LTE period. Frequency distributions and individual listings of all

adverse events and laboratory marked abnormalities will be generated based on As Treated population. The results will be presented by treatment groups.

Immunogenicity

The incidence of a positive response of anti-BMS-931699 antibodies during the LTE period will be summarized by treatment groups.

Pharmacokinetic Analyses

The descriptive summary of PK parameters will be provided by visits and by treatment groups during the LTE period.

Pharmacodynamic Analyses

The descriptive summary of selected PD and selected biomarkers will be provided by visits and by treatment groups during the LTE period.

Outcomes Research Analyses

Not applicable.

The details of the analyses, endpoints and grouping schemes (treatment groups) will be provided in the long-term statistical analysis plan (LTE SAP).

■

[REDACTED]

■

[REDACTED]

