8.3.2.3 Pharmacokinetic Endpoints

Ctrough: Trough level serum concentration of BMS-931699 at time points specified in Section [5.5](#).

8.3.2.5 *Immunogenicity*

Proportion of subjects with BMS-931699 induced antibody response at visit specified in [Table 5.5.3](#).

8.4 *Endpoints for Long-term Extension Period*

During the LTE period, the following endpoints will be assessed cumulatively (safety) and over time (efficacy).

8.4.1 *Safety Endpoints*

- Incidence and severity of all Adverse Events (AEs), Serious AEs, and pre-established Events of Special Interest
- Incidence and severity of clinically significant abnormalities in general laboratory tests

8.4.2 *Efficacy Endpoints*

- Proportion of subjects who achieve BICLA response (BICLA response rate)
- Proportion of subjects who meet response criteria for the SLE Responder Index (SRI) [SRI(4), SRI(5) and SRI(6)]

- CLASI score
- ACR 28 joint count of tender and swollen joints
- Overall BILAG-2004 score
- Overall SLEDAI-2K score
- Overall MDGA score
- The cumulative corticosteroid and immunosuppressant use
- Proportion of patients reaching a Major Clinical Response and Partial Clinical Response
- Fatigue, based on the FACIT
- Quality of life, based on SF-36

8.4.3 *Pharmacokinetic Endpoints*

Ctrough: Trough level serum concentration of BMS-931699 at time points specified in Section 5.5.

8.4.5 *Immunogenicity*

Proportion of subjects with BMS-931699 induced antibody response at visits defined in Table 5.1-3

8.5 *Analyses for the Short-Term Period*

8.5.1 *Demographics and Baseline Characteristics*

Frequency distributions of gender and race will be tabulated. Summary statistics for age, body weight, height, and Body Mass Index (BMI) will be tabulated.

8.5.2 *Efficacy Analyses*

Primary efficacy analysis:

The Chi-square tests will be used to compare the BICLA response rates at Day 169 between each of the active treatment arms and the placebo arm. The Chi-square p-value will be provided for each comparison between the active treatment and the placebo arm. In addition, the difference of the response rates between each active treatment and the placebo will be estimated and their corresponding 90% confidence interval will be calculated. No adjustment will be made for multiplicity.

Secondary efficacy analysis:

- Proportion of subjects who meet response criteria for the SLE Responder Index(4) [SRI(4)], SRI(5) and SRI(6) at Day 169

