8.7.1.3 Efficacy Analyses

For continuous secondary endpoints (eg, SLEDAI, MDGA etc.) point estimates and 90% confidence intervals for mean change from baseline to subsequent time points (in LTE period) within each treatment groups will be provided. For binary endpoints (BICLA Response, SRI(X) etc.), point estimates and 90% confidence intervals (CIs) will be provided using normal

approximation within each treatment group. The assessment windows for LTE period will be based on the first LTE dose date; the baseline to assess responses or changes still refers to the Day 1 assessment (the same as the baseline in the short-term period). The results will be presented by treatment groups. All analyses will be based on as-observed data; hence no imputation will be implemented. No statistical testing including p-value computation will be performed.

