8.7.1.8 Outcomes Research Analyses

Not applicable.

The details of the analyses, endpoints and grouping schemes (treatment groups) will be provided in the long-term extension statistical analysis plan (LTE SAP).

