**Table 7.1-1: Planned Efficacy Analyses**

Measure of Interest (Primary and Secondary Efficacy Endpoints):	Analysis Method
Counts]	

The Chi-square tests will be used to compare the BICLA response rates at Day 169 between each of the active treatment arms and the placebo arm. The Chi-square p-value will be provided for each comparison between the active treatment and the placebo arm. In addition, the difference of the response rates between each active treatment and the placebo arm will be estimated and their corresponding 90% confidence interval will be calculated. No adjustment will be made for multiplicity.

For each of the binary endpoints, the estimate and its corresponding 90% confidence interval will be calculated for the difference of the proportions between each active treatment arm and the placebo arm at the specified visit, similar to the primary analysis except no p-values will be provided.

The construction of confidence intervals for binary variables will be based on normal approximation if the number of the events in each individual treatment arm is at least 5. Otherwise, confidence interval using an exact method will be provided. The exact confidence intervals for binary variable within treatment group and between treatment groups will be constructed.

For each of the continuous endpoints, the mixed model will be fit with treatment, visit, and treatment-by-visit interaction as the fixed effects and measurements within each subject as the repeated measurements. The baseline value will be added into the model as a covariate if necessary. Based on the mixed model, the estimate and 90% confidence interval will be calculated for the difference between each active treatment and the placebo at each specified visit.

The results will be presented by the following grouping scheme in different periods, unless otherwise specified.

- **Pre-treatment period**: Only one group: All enrolled subjects.
- **Short-term period (ST)**: The results will be presented by treatment groups.

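### The protocol prescribes normal-approximation 90% intervals for long-term extension response rates with no small-count alternative, so they are too narrow on average in small groups and degenerate at 0% or 100% response (minor).

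*Protocol*

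**What the plan says.** The protocol synopsis (analyses for the LTE period, efficacy) states that for BICLA, SRI(X) and similar endpoints "point estimates and 90% confidence intervals (CIs) will be provided using normal approximation within each treatment group". Protocol 8.7.1.3 repeats the rule. Neither place sets a minimum count. Section 8.7.1.3 adds "All analyses will be based on as-observed data; hence no imputation will be implemented" and "No statistical testing including p-value computation will be performed". The LTE binary endpoints in protocol 8.4.2 include BICLA, SRI(4), SRI(5), SRI(6) and "Proportion of patients reaching a Major Clinical Response and Partial Clinical Response".

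SAP 7.1 treats the short-term period differently. It keeps the normal approximation only if each arm has at least 5 events. "Otherwise, confidence interval using an exact method will be provided". SAP 2.1 limits that document to the short-term period, so this safeguard does not extend to the LTE.

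The protocol closes its LTE section with "The details of the analyses, endpoints and grouping schemes (treatment groups) will be provided in the long-term extension statistical analysis plan (LTE SAP"). That plan was not available for this review.

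**The concern.** The short-term analysis, planned at 70 per arm, has a small-count rule. The LTE, where groups can become much smaller, has none in the protocol. Participation is optional (protocol 3.1), there is no defined end date (3.2), and denominators are observed counts, so they fall as subjects leave. Placebo subjects are re-randomised to the active arms, and if they are shown separately those groups are small from the start. Demanding endpoints may have few responders. Late visits, which include only subjects who stay on treatment, may have few non-responders. The normal approximation is weak in both situations.

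At stake is the honesty of the stated precision for LTE response rates. With testing ruled out, these intervals are the planned measure of uncertainty for those rates.

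**Working it through.** **The plan's own figures.** The documents give no LTE group size, coverage or interval width to reproduce. The nearest figure is the short-term power in protocol 8.1 (70 per arm, one-sided 0.05, continuity-corrected, placebo rate 25%). With effective n = (n − 1/d)²/n:
- 25% against 50%: (70 − 4)²/70 = 62.2, power 90.0% (stated: at least 89%).
- 25% against 45%: (70 − 5)²/70 = 60.4, power 75.0% (stated: 74%).

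These agree, so 25-50% is a fair planning range for response rates.

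**Group sizes (assumed).** At most 70 per active arm as randomised. Placebo switchers: at most 70/4 = 17.5 per active arm if four arms remain and switchers are shown separately. Pooled: at most 70 + 17.5 = 87.5. Late visits will have fewer. True rates of 10% and 90% are also assumptions; no document gives them.

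**Method.** For x responders of n, p̂ = x/n, the normal-approximation (Wald) interval is p̂ ± 1.645·√(p̂(1 − p̂)/n). Exact coverage at true rate p is the sum of binomial probabilities over all x whose interval contains p.

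**Worked case, n=17, p=25%.** The interval for x=2 is −1.1% to 24.6% and misses. Those for x=3 (2.4% to 32.9%) and x=7 (21.5% to 60.8%) contain 25%. That for x=8 (27.1% to 67.0%) misses. Coverage = P(3) + … + P(7) = 0.1893 + 0.2209 + 0.1914 + 0.1276 + 0.0668 = 79.6%. Wilson also covers at x=2 (4.0% to 30.1%), which adds 0.1136 and gives 91.0%.

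**Worked case, n=10, p=90%.** Wald covers for x = 7, 8, 9: 0.0574 + 0.1937 + 0.3874 = 63.9%. All ten respond with probability 0.9¹⁰ = 34.9%, and the interval is then 100% to 100%.

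| n | True rate | Wald | Wilson | Clopper-Pearson | Chance of zero width |
|---|---|---|---|---|---|
| 10 | 25% | 92.4% | 86.6% | 98.0% | 5.6% |
| 10 | 90% | 63.9% | 93.0% | 98.7% | 34.9% |
| 17 | 25% | 79.6% | 91.0% | 95.2% | 0.75% |
| 17 | 90% | 81.1% | 91.7% | 97.8% | 16.7% |
| 30 | 10% | 79.0% | 88.4% | 93.2% | 4.2% |
| 30 | 25% | 85.1% | 91.2% | 94.1% | 0.02% |
| 70 | 25% | 89.0% | 90.4% | 92.6% | about 0 |
| 70 | 50% | 88.0% | 88.0% | 92.8% | about 0 |

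Mean coverage over true rates of 25-50%:

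| n | Wald | Wilson | Clopper-Pearson |
|---|---|---|---|
| 10 | 84.0% | 90.0% | 95.0% |
| 17 | 86.3% | 90.1% | 94.2% |
| 30 | 88.3% | 89.8% | 93.3% |
| 70 | 89.3% | 90.1% | 92.4% |

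**Impossible limits.** Wald gives −5.6% to 25.6% for 1/10, and 84.7% to 103.5% for 16/17.

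**Would the short-term rule repair this?** Only at the low end, because it counts events and not non-events. At n=17 and a true rate of 90% it still covers 81.1%, and 17/17 still has zero width. An exact interval whenever responders or non-responders number fewer than 5 covers 97.8% there.

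**The case against.** The strongest objection is that the LTE SAP is unseen. The protocol defers LTE details to it, and in the short-term period the small-count rule appears only in the SAP, so this sponsor may well put such rules there. SAP 8.1.3 also leaves the handling of Major and Partial Clinical Response to that document. This stands as a limit: a missing fallback is shown for the protocol only. It does not remove the point, because the protocol does not leave the method open. An LTE SAP that follows the protocol inherits the weakness, and one that departs from it creates a discrepancy.

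A reader might infer that every LTE response-rate interval under-covers and that intervals collapse as groups shrink. The documents and the arithmetic do not support that. Zero width needs none or all to respond, which is rare at the planning rates of 25-50%. Coverage is uneven and sometimes above nominal (92.4% at n=10 and 25%, where Wilson gives 86.6%). Pooling placebo switchers could start groups near 87. A reader might also infer that these are the LTE's only intervals, but the continuous endpoints have 90% intervals for mean change.

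Finally, little depends on the choice. The LTE analysis is descriptive, without p-values and without interim analyses for dose adaptation, and reported counts would reveal a 0/n or n/n result. That is why the point is minor.

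**Conclusion.** The point holds in limited form. The protocol names a method with no small-count condition for groups that may become small, and followed as written it gives intervals that are too narrow on average there. Over rates of 25-50%, the mean shortfall from 90% is 6.0 points at n=10, 3.7 at n=17, 1.7 at n=30 and 0.7 at n=70. At extreme rates it is much larger: 26.1 points at n=10 and a true rate of 90%. These sizes rest on assumed LTE group sizes and, for 10% and 90%, on assumed rates. Whether the LTE SAP already corrects the method cannot be determined from the documents. No test, decision or short-term result is affected. Severity is minor.

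**What to change.** In protocol 8.7.1.3 and the matching synopsis paragraph, and in the LTE SAP if it repeats the rule, replace the normal approximation with Wilson score 90% intervals (or Clopper-Pearson) for every LTE proportion. An acceptable alternative is an exact interval whenever responders or non-responders number fewer than 5. Do not simply import the events-only rule of SAP 7.1. If the LTE SAP already has an adequate rule, align the protocol wording with it.

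The cost is one phrase and a standard software option, with no effect on design, sample size or data collection. Intervals become somewhat wider where counts are sparse: 0/10 changes from zero width to 0-21.3% (Wilson) or 0-25.9% (Clopper-Pearson), and 17/17 to 86.3-100% or 83.8-100%. Clopper-Pearson is conservative (mean coverage 95.0% at n=10 over rates of 25-50%). Wilson averages about 90% but can fall below it at particular rates.
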